**Subject Eligibility Criteria**

*Inclusion criteria:*

- 1)** Age 18-65;
- 2)** Nicotine dependent as assessed by DSM-V;
- 3)** Reported daily cigarette consumption  $\geq 10$  and expired carbon monoxide (CO) measurement of  $\geq 10$  ppm;
- 4)** Fagerstrom Test of Nicotine Dependence (FTND)  $\geq 4$ ;
- 5)** Reported motivation to quit within 30 days as assessed using the Contemplation Ladder score of  $\geq 7$ .

*Exclusion criteria:*

- 1)** Reported smoking abstinence in the 3 months preceding screening visit;
- 2)** Current use of other smoking cessation aids;
- 3)** Allergy and/or contraindication to varenicline or rTMS;
- 4)** Pregnancy, trying to become pregnant or breastfeeding;
- 5)** Current or recent history of cardiovascular or cerebrovascular disease and/or current hypertension;
- 6)** Current or historical evidence of suicidal behavior;
- 7)** Serious current or personal history of medical condition/disease (neurological disorders, brain lesions, multiple sclerosis, head trauma, loss of consciousness, hearing loss, etc.);
- 8)** Current, personal history or family history of seizures;
- 9)** Cognitive impairment as defined as a Mini Mental State Examination (MMSE) score  $<24$ ;
- 10)** Concomitant use of medication that lowers seizure threshold.

## Consent

All subjects will provide written informed consent prior to study enrolment. i.e. before undergoing any study-related procedures.

## Sample Size and Power Calculation

Based on the results of a recently completed multi-centre trial [4] and results from our previous trial investigating varenicline's efficacy in patients in a residential drug program, we anticipate a 12 week abstinence point prevalence rate of approximately 40% following treatment with varenicline. To detect a clinically relevant 30% difference in the proportion of abstinence between active deep rTMS and sham rTMS treatments with a power of 0.80 ( $\alpha = 0.05$ ), we would need  $n=42$  participants per study arm. However, in light of the pilot nature of this proposed study and the allotted time frame for study completion, we will recruit  $n=25$  participants per study arm (power = 0.66). However, we anticipate attrition with this study sample and as such, we will recruit  $n=30$  per arm to obtain 50 completers in total.

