## Study Design

Overview: This study will be a randomized, double-blind, sham-controlled clinical trial. Specifically, fifty nicotine dependent participants expressing a willingness to quit smoking will be randomized into one of two rTMS intervention arms: Sham (n=25) or Active (10 Hz, n=25). All participants will receive an open-label treatment of varenicline (Week 1 to Week 12), and a target quit date (corresponding to the end of Week 2) will be set for each individual. Participants will also receive brief weekly counselling adapted from the Mayo Clinic's 'Smoke Free and Living It' manual. The rTMS interventions will begin at Week 1 for four weeks (5 sessions a week for a total of 20 sessions), and will be performed with an insula-targeting H-coil. Moreover, follow-up visits will be scheduled weekly for the duration of the medication phase and on Week 26. The primary outcome of the proposed study will be plasma cotinine verified (<15 ng/ml) 7-day point prevalence abstinence as measured at the end of Week 12. Other smoking outcomes (craving, consumption patterns, and dependence) will be captured through standardized questionnaires throughout the study duration. Participants will also have plasma cotinine verified measurements of abstinence at the end of rTMS treatment (end of Week 4), and at the follow-up at 6 months (end of Week 26). This trial will be conducted in compliance with the protocol, GCP, and Canadian Food and Drug Regulations Division 5.

Participants: Participants in the proposed study will be nicotine dependent individuals (n=50). We will recruit through various sources: the community, CAMH clinics, word of mouth, and/or through posters/fliers distributed in and around the research centers as well as on the CAMH website. CAMH approved study recruitment ads will be placed primarily around, but not limited to, the downtown Toronto area. Ads may also be placed in various local newspapers, magazines, community venues (e.g., bars) as well as TTC streetcars, buses and subways. Online advertisement services may be employed, in accordance with CAMH guidelines. Ads and fliers will be approved by the REB. Participants may also be recruited from similar protocols approved at CAMH provided they have agreed to being contacted about future studies.

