Participants will be randomized into either sham (n=25) or active (10Hz, n=25) rTMS intervention in a 1:1 ratio. Brainsway will provide the randomization cards and the randomization list, which will then be managed by an independent person outside of the study. The stimulation protocol will begin in Week 1, and will consist of 5 rTMS sessions per week over the course of 4 weeks (20 in total). Importantly, rTMS will be administered 2 weeks preceding and 2 weeks following the targeted quit date (Day 15), as smokers are believed to be most susceptible to relapse early in the abstinence phase [46]. Both active and sham stimulations will be administered using the insula H-Coil (Brainsway, Model 102B; Jerusalem, Israel), developed by [name] (consultant on this proposal). First, resting motor threshold (RMT) will be determined based on the minimum intensity to cause one of the right hand muscles to activate in at least 5 of 10 trials. The active simulation will comprise of 34 trains of 3 seconds each at 10 Hz and 30 pulses per train and an inter-train interval of 26 seconds. Stimulation intensity will be administered at a target of 120% RMT. Titration of stimulus intensity may occur over the first 4 sessions to enhance tolerability. For participants with poor tolerability the stimulation target will be a minimum of 110% RMT. For the sham stimulation, we will use the same coil placement as that used for active stimulation, matching the number of pulses delivered. The sham coil, which is built into the same helmet, mimics the active coil with respect to acoustics and scalp sensation. Notably, this coil, which allows for the bilateral stimulation of the insular cortex, is presently located at CAMH, and has been used by our team in a recently completed pilot study in healthy controls. Since rTMS sessions will occur daily for 4 weeks, medical staff will be onsite during all procedures and standard procedures for treating patients with rTMS in the Temerty Centre will followed.

*Follow-up Visits:*

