## Data Analysis

Descriptive statistics will be used to compare groups (Sham, rTMS) at baseline on main clinical and demographic variables. Fisher's Exact and Mann-Whitney U test will be used for categorical and continuous variables, respectively. Subjects with missing values in the primary outcome (abstinence at 4, 12 or 26 weeks) will be compared with completers on baseline characteristics, to help in the understanding of the reasons for missing values, if at least 10 subjects (20%) are found to be missing. Mixed effect logistic regression that uses abstinence at 4, 12 and 26 weeks as dependent variables will be adjusted to the data, with groups and categorical time (4, 12 and 26 weeks) specified as fixed effect, and subject intercepts as random effects. Baseline variables correlated with missingness and/or known to be associated with the outcome will be added as covariates with focus on model parsimony (not to include many covariates) due to small sample size. The primary hypothesis will be tested using a contrast that compares abstinence at week 12 in the logit scale. Similarly, abstinence will also be compared at weeks 4 and 26 as part of our secondary objectives. Mixed effect models that uses maximum likelihood estimation accounts for missingness in the dependent variable by using all available information in the estimation, under the MAR assumption (Missing At Random – the values of a data points are not associated with the missing status of the data point after accounting for relevant covariates) [49]. Other measures related to our secondary objectives (e.g., FTND, CO, TLFB, etc.) will also be analyzed using linear mixed or generalized mixed models, depending on the nature of the outcome of interest. Graphs will be used to explore the data, the models assumptions (for example, residual plots), as well as model results (for example, estimated means plot). Due to small sample, effect sizes with 95% confidence intervals as well as standardized effect sizes will be reported.

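### The stated power of 0.66 at 25 per arm does not fit the stated 42 per arm for power 0.80; the methods that give 42 give 0.57 to 0.58 at 25

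*Combined protocol and SAP*

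**What the plan says.** The Sample Size and Power Calculation section expects week-12 point prevalence abstinence of "approximately 40% following treatment with varenicline". It aims to detect a "clinically relevant 30% difference in the proportion of abstinence between active deep rTMS and sham rTMS treatments" with power 0.80 and alpha 0.05, and gives 42 per arm. Citing the pilot nature of the study and the time available, it then reduces the size to 25 "participants per study arm (power = 0.66"). It goes on to plan for 30 "per arm to obtain 50 completers in total". Neither the test nor its sidedness is named.

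The number 25 per arm also appears as the number randomised. The Study Design overview has participants "randomized into one of two rTMS intervention arms: Sham (n=25) or Active (10 Hz, n=25"), and the rTMS paragraph says "Participants will be randomized into either sham (n=25) or active (10Hz, n=25) rTMS intervention in a 1:1 ratio".

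On the test itself, the Data Analysis section says: "The primary hypothesis will be tested using a contrast that compares abstinence at week 12 in the logit scale". The contrast comes from a mixed-effect logistic model.

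**The concern.** One set of assumptions is followed by two results: a sample size for power 0.80 and a power for a smaller sample. Once the rates, alpha and method are fixed, the first result determines the second. Cutting the sample from 42 to 25 per arm removes about 40% of the information (1 − 25/42 = 0.405), and a fall in power from 0.80 to only 0.66 looks too small for that.

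This is the only power figure given for 25 per arm, the size the plan says it will randomise and expects to complete. Anyone weighing a null result would take the chance of missing the target difference as 34%. If the figure is wrong, it errs in the favourable direction.

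**Working it through.** **Inputs.** From the Sample Size and Power Calculation section: sham rate 0.40, difference 0.30 (read as absolute, so active rate 0.70), alpha 0.05, target power 0.80. From the rTMS paragraph: 1:1 allocation. Sidedness is not stated. Two-sided is assumed first because it reproduces the plan's 42.

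**Step 1: reproduce 42 per arm.**

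Pooled z, with mean rate 0.55:
- null term: √(2 × 0.55 × 0.45) = √0.495 = 0.7036
- alternative term: √(0.40 × 0.60 + 0.70 × 0.30) = √0.45 = 0.6708
- n = (1.960 × 0.7036 + 0.842 × 0.6708)² / 0.30² = 1.944² / 0.09 ≈ 42.0

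Arcsine, with h = 2·asin√0.70 − 2·asin√0.40 = 0.6129:
- n = 2 × (2.802 / 0.6129)² = 41.8, rounded up to 42

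Both methods give 0.79 at 41 and 0.80 at 42. The plan's first figure is reproduced, which supports the reading of 40% versus 70%, two-sided.

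**Step 2: same methods, same inputs, 25 per arm.**
- Pooled z: (0.30 × √25 − 1.960 × 0.7036) / 0.6708 = (1.500 − 1.379) / 0.6708 = 0.180; power Φ(0.180) = 0.572
- Arcsine: 0.6129 × √(25/2) − 1.960 = 2.167 − 1.960 = 0.207; power Φ(0.207) = 0.582

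**Step 3: try other tests.** Power at 40% versus 70%:

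| Method | 25 per arm | 30 per arm | 42 per arm |
|---|---|---|---|
| Pooled z, two-sided | 0.572 | 0.653 | 0.800 |
| Arcsine, two-sided | 0.582 | 0.660 | 0.802 |
| Unpooled z, two-sided | 0.609 | 0.688 | 0.826 |
| Pearson chi-square, two-sided, exact enumeration | 0.622 | 0.663 | 0.828 |
| Logit Wald, two-sided, exact enumeration | 0.564 | 0.66 | 0.800 |
| Fisher, two-sided | 0.506 | 0.561 | 0.764 |
| Pooled z, one-sided | 0.695 | 0.766 | 0.880 |
| Fisher, one-sided | 0.622 | 0.665 | 0.828 |

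Every two-sided test is below 0.66 at 25. One-sided pooled z exceeds 0.66 at 25 but needs only 33 per arm for 0.80, so it contradicts 42. The one-sided logit Wald formula comes closest to 0.66 at 25 (0.674), but it gives 0.858 at 42.

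**Step 4: a check that does not use the assumed rates.** On the normal approximation the standardised effect grows with √n. If power is 0.80 at 42 per arm:
- two-sided: 2.802 × √(25/42) − 1.960 ≈ 0.201; power at 25 is 0.58
- one-sided: (1.645 + 0.842) × √(25/42) − 1.645 ≈ 0.273; power at 25 is 0.61

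In reverse, if 0.66 held at 25 per arm (z = 0.412), the size for power 0.80 would be:
- two-sided: 25 × (2.802 / 2.372)² = 34.9, about 35 per arm
- one-sided: 36.5, about 37 per arm

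Neither is 42.

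**Step 5: where 0.66 does fit.** Scaling two-sided from 42 per arm, power 0.66 needs 42 × (2.372 / 2.802)² ≈ 30 per arm. The table agrees: at 30 per arm, pooled z gives 0.653 and arcsine 0.660. Thirty is the number the section plans to recruit per arm. That 0.66 was computed for 30 is an inference; the mismatch does not depend on it.

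**The case against.** **The size of the gap depends on the test, which the plan does not name.** This is fair. Exact enumeration of the two-sided Pearson chi-square first reaches 0.80 at 41 per arm and gives 0.622 at 25, a gap of about 4 points. A one-sided exact chi-square with rates changed to 45% versus 71.5% gives 0.80 at 42 and 0.636 at 25, a gap of about 2.4 points, but those are not the plan's rates. The figure of 8 to 9 points belongs to the pooled z and arcsine formulas, which reproduce 42 exactly from the plan's inputs. None of these alternatives reaches 0.66.

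**Thirty per arm will be recruited, and the mixed model uses partial data under a missing-at-random assumption.** This also has force. If non-completers contribute information, power lies between the values for 25 and 30 per arm: 0.57 to 0.65 (pooled) or 0.58 to 0.66 (arcsine). But 0.66 is then the upper limit, reached only if the attrition the plan expects costs no information, and the text attaches 0.66 to 25.

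**The planned test is a mixed-logistic contrast, which two-proportion formulas only approximate.** True, but the single-time-point logit Wald test, the closest simple analogue, gives 0.800 at 42 and 0.564 at 25. It does not support 0.66 either.

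**Nothing turns on it.** The plan calls the study a pilot, says 42 per arm would be needed and commits to 95% confidence intervals. This limits the consequence but does not make the number right.

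**Conclusion.** The concern holds. With 40% versus 70%, two-sided alpha 0.05 and the methods that reproduce 42 per arm, power at 25 per arm is 0.57 (pooled z) or 0.58 (arcsine), not 0.66. The type II error is about 42 to 43% instead of 34%. Across the two-sided tests in the table, power at 25 runs from 0.51 to 0.62. The conclusion that the two stated figures disagree survives every test and sidedness tried; only the size of the gap varies.

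At 25 per arm against a 40% sham rate, power 0.66 would need an active rate of about 73%, and power 0.80 about 78%, instead of the planned 70%.

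This should be corrected because the plan claims more power than its own assumptions deliver. It does not change the sample size, the analysis or the plan's own description of the trial as a pilot with power below 0.80.

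**What to change.** In the Sample Size and Power Calculation section, replace the power of 0.66 at 25 per arm with 0.57 (two-sided pooled two-proportion z test, 40% versus 70%), or with 0.58 if the arcsine method was used. State the test and sidedness behind both the 42 per arm and the power figure, and note that they approximate the planned week-12 mixed-logistic contrast. If some other method was used, name it and correct whichever of the two figures it does not support. Quote 0.65 (pooled) or 0.66 (arcsine) only for 30 evaluable participants per arm.

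Optionally, add the expected 95% confidence interval half-width for the difference at 25 per arm: 1.96 × √((0.24 + 0.21) / 25) = 0.263, about 26 percentage points.

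The cost is one sentence in the protocol and a less favourable stated power. No further participants are needed.

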## Data Analysis

Descriptive statistics will be used to compare groups (Sham, rTMS) at baseline on main clinical and demographic variables. Fisher's Exact and Mann-Whitney U test will be used for categorical and continuous variables, respectively. Subjects with missing values in the primary outcome (abstinence at 4, 12 or 26 weeks) will be compared with completers on baseline characteristics, to help in the understanding of the reasons for missing values, if at least 10 subjects (20%) are found to be missing. Mixed effect logistic regression that uses abstinence at 4, 12 and 26 weeks as dependent variables will be adjusted to the data, with groups and categorical time (4, 12 and 26 weeks) specified as fixed effect, and subject intercepts as random effects. Baseline variables correlated with missingness and/or known to be associated with the outcome will be added as covariates with focus on model parsimony (not to include many covariates) due to small sample size. The primary hypothesis will be tested using a contrast that compares abstinence at week 12 in the logit scale. Similarly, abstinence will also be compared at weeks 4 and 26 as part of our secondary objectives. Mixed effect models that uses maximum likelihood estimation accounts for missingness in the dependent variable by using all available information in the estimation, under the MAR assumption (Missing At Random – the values of a data points are not associated with the missing status of the data point after accounting for relevant covariates) [49]. Other measures related to our secondary objectives (e.g., FTND, CO, TLFB, etc.) will also be analyzed using linear mixed or generalized mixed models, depending on the nature of the outcome of interest. Graphs will be used to explore the data, the models assumptions (for example, residual plots), as well as model results (for example, estimated means plot). Due to small sample, effect sizes with 95% confidence intervals as well as standardized effect sizes will be reported.

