## Outcome Measures

Main Outcome Measure: 7-day point prevalence abstinence at the end of 12 weeks. This outcome will be measured by self-report of abstinence for the past 7 days, and confirmed using a plasma cotinine measurement of  $\leq 15$  ng/ml

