## Secondary Outcome Measures:

1) Fagerstrom Test of Nicotine Dependence (FTND). The FTND will be used to assess physical

dependence severity in participants [40].

2) Expired Carbon Monoxide (CO) Measurements. Expired CO measurements will be regularly taken as a biological confirmation of recent smoking.

3) Cigarettes per day. The Timeline Follow-Back (TLFB) will be used to determine daily self-reported cigarette consumption [42].

4) Minnesota Nicotine Withdrawal Scale (MNWS). The MNWS will be used to assess tobacco withdrawal symptoms [50].

5) Tiffany Questionnaire of Smoking Urges (T-QSU). The T-QSU will be used to assess symptoms of craving/urges for tobacco [51].

6) Point prevalence abstinence at end of 4 weeks: This outcome will be measured by self-report of abstinence for the past 7 days and confirmed using a plasma cotinine measurement of <15 ng/ml.

7) Prolonged abstinence from end of treatment (Week 12) to end of follow up (Week 26). This outcome will be measured by self-report of continuous abstinence since the last visit (at Week 12) and confirmed using a plasma measurement of <15 ng/ml.

8) Prolonged abstinence with 2-week grace period at end of follow up (Week 26). This outcome will be measured by self-report of continuous abstinence since Week 4 and confirmed using a plasma measurement of <15 ng/ml.

9) Continuous abstinence at 6 months: This outcome will be measured by self-report of continuous abstinence since the target quit day (Week 2) and confirmed using a plasma measurement of <15 ng/ml.

The FTND, T-QSU and MNWS will be administered weekly for the first month (i.e. 4 weeks) and subsequently at 8, 12 and 26 weeks.

In the case that a participant declines blood draws, urine will be collected instead for the quantification of cotinine levels.

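### The primary week-12 contrast comes from a model with no listed group-by-time term, so it pools weeks 4, 12 and 26, and the week-26 abstinence response in that model is not settled

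*Combined protocol and SAP*

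**What the plan says.** Data Analysis describes one joint model: "Mixed effect logistic regression that uses abstinence at 4, 12 and 26 weeks as dependent variables". Its structure is given as "with groups and categorical time (4, 12 and 26 weeks) specified as fixed effect, and subject intercepts as random effects". No group-by-time term is listed. The primary hypothesis is tested by a week-12 contrast on the logit scale taken from this model, and the section continues: "Similarly, abstinence will also be compared at weeks 4 and 26 as part of our secondary objectives".

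The type of abstinence is not named in that section. Elsewhere:

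- **Week 12:** "Main Outcome Measure: 7-day point prevalence abstinence at the end of 12 weeks" (Outcome Measures).
- **Week 4:** "Point prevalence abstinence at end of 4 weeks", also over the past 7 days (Secondary Outcome Measures, item 6).
- **Week 26:** three outcomes, none of them point prevalence (Secondary Outcome Measures). Item 7 is prolonged abstinence from week 12, measured by "self-report of continuous abstinence since the last visit (at Week 12"). Item 8 is prolonged abstinence since week 4. Item 9 is continuous abstinence since the target quit day.

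Aims and Hypotheses follows the same split: point prevalence is the short-term measure, and prolonged and continuous abstinence are the week-26 measures. On the other side, Data Analysis applies the primary-outcome label to all three weeks: "Subjects with missing values in the primary outcome (abstinence at 4, 12 or 26 weeks").

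**The concern.** Two gaps in the same model bear on the primary result.

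First, with group and time as the only fixed effects, the model has a single group coefficient shared by all visits. A contrast labelled week 12 is then an average effect over weeks 4, 12 and 26. The primary hypothesis concerns the end of varenicline treatment. A difference that appears only at follow-up should not be able to reject it.

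Second, the model needs a response at week 26, and the plan offers three candidates of a different kind from the week-4 and week-12 response. Items 8 and 9 look back over earlier visits, so week 26 would be partly fixed by the earlier responses. A random-intercept model instead assumes that the three responses are independent given the subject's intercept. The section also promises that "Due to small sample, effect sizes with 95% confidence intervals as well as standardized effect sizes will be reported", so in this small trial the estimate matters as much as the test.

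**Working it through.** **The plan's own figure.** Sample Size and Power Calculation assumes 40% against 70% at week 12, two-sided alpha 0.05 (sidedness is not stated; two-sided reproduces the figure) and power 0.80. With the mean rate 0.55:

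n = [1.960 × √(2 × 0.55 × 0.45) + 0.842 × √(0.40 × 0.60 + 0.70 × 0.30)]² / 0.30² = (1.379 + 0.565)² / 0.09 ≈ 42 per arm.

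This matches the plan. It rests on week-12 point prevalence alone and does not change under anything below.

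**Step 1: what the listed model estimates.** For subject i in group g (0 or 1) at week t:

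logit P(Y = 1 | b) = α_t + β·g + b, with b ~ N(0, SD²).

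The group contrast at week t is (α_t + β + b) − (α_t + b) = β for t = 4, 12 and 26. The three planned contrasts are therefore the same number with the same p-value. With a group-by-time term, β becomes β_4, β_12 and β_26. That is three group parameters instead of one, so two more.

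**Step 2: size of the leak from week 26.** Assumed: 40% in both arms at weeks 4 and 12; 30% against 60% at week 26 as point prevalence; SD 2; 25 per arm; no missing data; 800 simulated trials; Wald test at 0.05.

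| Model | Rejection at week 12 |
|---|---|
| Group + time, as listed | 0.144 |
| Group-by-time | 0.046 |

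The simulation error is √(0.144 × 0.856 / 800) ≈ 0.012 for the first and √(0.046 × 0.954 / 800) ≈ 0.007 for the second. A separate refit of the scenario gave 15% against 5%. In that refit the group + time model reports a week-12 log odds ratio of 0.65 (odds ratio e^0.65 ≈ 1.9) where the true value is 0.

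**Step 3: which week-26 response.** Take the patterns (week 4, week 12, week 26), with 1 for abstinent, and assume that cotinine agrees with self-report. Item 9 rules out 001, 011 and 101, which is 3 of 8. Item 8 rules out 001 and 101, which is 2 of 8. Item 7 rules out the same two if it requires abstinence at week 12 (the strict reading). The loose reading of item 7 requires only no lapse after week 12 and rules out none. The model gives all 8 patterns positive probability.

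**Step 4: effect of that choice on the week-12 estimate.** Assumed: 40% against 70% at weeks 4 and 12; 30% against 60% at week 26; true SD 2; probability of no lapse 0.70-0.95 per interval. Maximum likelihood fit to expected cell counts, with group-by-time.

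| Week-26 response | Week-12 log odds ratio | Conditional odds ratio | Fitted SD |
|---|---|---|---|
| Point prevalence | 2.05 | 7.8 | 2.0 |
| Item 7, loose | 1.89-2.02 | 6.6-7.5 | 1.74-1.94 |
| Item 7, strict | 2.28-2.49 | 9.8-12.1 | 2.37-2.68 |
| Item 8 | 2.16-2.44 | 8.6-11.5 | 2.18-2.61 |
| Item 9 | 2.29-2.76 | 9.9-15.8 | 2.38-3.07 |

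Over true SD 1-3, the odds ratio relative to point prevalence is 0.7-1.0 times (loose item 7), 1.2-1.7 (strict item 7), 0.98-1.54 (item 8) and 1.2-2.3 (item 9).

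With the random intercept integrated out, over the same SDs and all five responses, the fitted week-12 rates are 0.399-0.408 against 0.697-0.708. The risk difference is 0.298-0.301 and the population odds ratio 3.47-3.53. The direct value is (0.70/0.30) / (0.40/0.60) = 3.5.

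**Step 5: power.** With 25 per arm, group-by-time and a likelihood-ratio test, power is 0.58-0.63 for point prevalence, strict item 7, item 8 and item 9. The verdict differs among these four in 3-6% of trials. With a Wald test at SD 3 and no-lapse 0.95, power falls from 0.507 (point prevalence) to 0.392 (item 9). That loss goes with near-degenerate fits and disappears with the likelihood-ratio test.

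**The case against.** **The interaction was probably meant.** The plan asks for a contrast at week 12 and then, separately, at weeks 4 and 26. Those requests make sense only if the group effect may differ by week. This is a fair reading and probably the right one. It does not remove the gap: the fixed effects are listed, and the term is not among them.

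**Point prevalence at week 26 was probably meant.** The primary-outcome label on all three weeks, and the overview in Study Design, which promises cotinine-verified abstinence at weeks 4 and 26 directly after defining the primary outcome, both lean that way. The Summary of Events table cannot be read reliably enough to rule it in or out. But the week-26 comparison is also tied to the secondary objectives, which name only prolonged and continuous abstinence. The documents point both ways.

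**The harm from the week-26 choice is mostly one of scale.** This stands. A reader might infer from odds ratios of 7.8 against 15.8 that the primary effect, or the trial's power, hangs on the week-26 definition. It does not: the conditional odds ratio rises because the fitted SD rises, while the week-12 rates and risk difference stay put. The unknown SD alone moves the point-prevalence odds ratio from 4.5 to 14.9 (SD 1 to 3).

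**The excluded patterns are not impossible by definition.** Also correct. Items 8 and 9 name no earlier cotinine check, so a participant who failed cotinine at week 12 could still qualify on self-report.

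**Conclusion.** The point holds in two parts of unequal weight.

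The heavier part is the missing group-by-time term. That the listed model cannot isolate week 12 follows from its form and needs no assumptions. The rejection rate of about 14-15% against 5% does need them: the rates in Step 2, SD 2, week 26 coded as point prevalence, and an effect confined to week 26. With strict item 7, item 8 or item 9 as the week-26 response, the listed model rejects in only 3-5% of such trials; with loose item 7 it rejects in 12.5%.

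The lighter part is the inconsistent week-26 response. Using item 8, item 9 or a strict item 7 misspecifies the joint model and generally raises the conditional week-12 odds ratio. It leaves the marginal week-12 effect and likelihood-ratio power almost unchanged. The figures in Steps 4 and 5 assume no missing data. A smaller simulation of 200 trials with 5%, 12% and 17% missing at weeks 4, 12 and 26, different rates and approximate standard errors compared continuous abstinence with point prevalence under group-by-time. It found p<0.05 discordant in 12% of trials, so the 3-6% should not be taken as a bound.

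The documents do not support saying that the sponsor chose a model without interaction, or that the trial's conclusion turns on the week-26 definition. Both gaps should be closed before unblinding.

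**What to change.** - Add a group-by-time term and take the primary contrast at week 12 from it.
- State that the response at weeks 4, 12 and 26 is cotinine-confirmed 7-day point prevalence abstinence. Week 26 can be derived from the Timeline Follow-Back, taken at every visit, and the cotinine sample already planned there.
- Analyse items 7, 8 and 9 in separate secondary models, and say whether item 7 requires abstinence at week 12.
- Reserve the primary-outcome label in Data Analysis for week 12.

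The first two changes belong together: without the interaction, point prevalence is the week-26 response most exposed to a week-26-only effect.

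The cost is one derived variable, two extra model parameters and some wording. The week-12 interval will be slightly wider than a pooled group effect would give. No new data collection is needed.
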